Protocol 2020-1241

19 October 2022

Abbreviation or special term	Explanation
ECHO	Echocardiogram
ECOG	Eastern Cooperative Oncology Group
eCRF	Electronic case report form
EMR	Electronic medical record
ER+	Estrogen receptor-positive
EOT	End-of-treatment
eSAE	Electronic serious adverse event application
FDA	Food and Drug Administration
GCP	Good Clinical Practice
HBV	Hepatitis B virus
HbcAb	Hepatitis B core antibody
HbsAg	Hepatitis B surface antigen
HCV	Hepatitis C virus
HR+	Hormone receptor-positive
IB	Investigator's brochure
IC50	Half-maximal inhibitory concentration
ICF	Informed consent form
ICH	International Council on Harmonisation
IHC	Immunohistochemistry
IM	Intramuscular(ly)
IND	Investigational new drug
IRB	Institutional review board
IV	Intravenous(ly)
Kd	Dissociation constant
MATE	Multidrug and toxin extrusion protein
MDACC	MD Anderson Cancer Center
MOCLIP	Molecular and Clinical Data Integrated Platform
MRI	Magnetic resonance imaging

Proprietary Information of MD Anderson

Protocol 2020-1241

19 October 2022

Abbreviation or special term	Explanation
mTOR	Mammalian target of rapamycin
MTD	Maximum tolerated dose
MUGA	Multigated acquisition
NCI	National Cancer Institute
NE	Not evaluable
NGS	Next-generation sequencing
NHL	Non-Hodgkin's lymphoma
ORR	Objective response rate
OS	Overall survival
PCR	Polymerase chain reaction
PD	Progressive disease
PET	Positron emission tomography
PFS	Progression-free survival
P-gp	P-glycoprotein
PI	Principal investigator
PI3K	Phosphatidylinositol-3 kinase
PI3Ki	Phosphatidylinositol-3 kinase inhibitor
PR	Partial response
PR+	Progesterone receptor-positive
PJP	Pneumocystis jiroveci pneumonia
RECIST	Response Evaluation Criteria in Solid Tumors
RNAseq	RNA sequencing
RP2D	Recommended Phase 2 dose
SAE	Serious adverse event
SD	Stable disease
SERD	Selective estrogen receptor degrader
SOC	Standard of care
TB	Total bilirubin

Proprietary Information of MD Anderson

Protocol 2020-1241

19 October 2022

Abbreviation or special term	Explanation
TCGA	The Cancer Genome Atlas
Treg	Regulatory CD4+ T-cell
ULN	Upper limit of normal
WBC	White blood cell

[figure not shown]
Proprietary Information of MD Anderson

Protocol 2020-1241

19 October 2022

CLINICAL STUDY SYNOPSIS

Protocol Title:	Phase 2 study of PI3K inhibitor copanlisib in combination with fulvestrant in selected ER+ and/or PR+ cancers with PI3K (PIK3CA, PIK3R1) and/or PTEN alterations
IND Number:	157719
Protocol Number:	21897/ 2020-1241
Principal Investigator:	[REDACTED]
Study Phase:	Phase 2
Investigational Products:	Copanlisib and fulvestrant
Study Indications:	Solid tumors: ovarian cancer, endometrial cancer, breast cancer
Study Centers:	MD Anderson Cancer Center (single-center study)

Length of study:	2 years
Objectives:	The objective of this phase 2 basket study is to evaluate the efficacy and safety of copanlisib in combination with fulvestrant administered to subjects with selected estrogen receptor-positive (ER+) and/or progesterone receptor-positive (PR+) advanced or metastatic solid tumors with PI3K and/or PTEN alterations. The study will have two parts. Part 1: Dose confirmation: [REDACTED]

Proprietary Information of MD Anderson

Protocol 2020-1241

[figure not shown]
19 October 2022

	
Secondary Objectives:
 
• To assess the efficacy of copanlisib administered in combination with fulvestrant as outlined in Part 2 by evaluating the objective response rate (ORR).• To evaluate additional efficacy measures such as progression-free survival (PFS) and overall survival (OS) of copanlisib in combination with fulvestrant. 
Exploratory Objective:
 
• To investigate clonal evolution, and mechanisms of resistance using tissue and liquid biopsies utilizing circulating tumor DNA (ctDNA) as outlined in Part 2. 
Part 2: Dose expansion:
 
Primary Objectives:
 
• To assess the efficacy of copanlisib administered in combination with fulvestrant as outlined above by evaluating the objective response rate (ORR). Patients enrolled for Part 1 will be included in this efficacy analysis. 
Secondary Objectives:
 
• To evaluate additional efficacy measures such as PFS and OS of copanlisib in combination with fulvestrant.• To evaluate the safety and tolerability of copanlisib in combination with fulvestrant. 
Exploratory Objective:
 
• To investigate clonal evolution, and mechanisms of resistance using tissue and liquid biopsies utilizing ctDNA.
Purpose/ Rationale:	
The purpose of this study is to evaluate the efficacy and safety of copanlisib in combination with fulvestrant in advanced hormone receptor-positive (HR+) solid tumors harboring alterations that activate the Phosphatidylinositol-3 kinase (PI3K) pathway. Copanlisib is a potent pan-PI3K inhibitor (PI3Ki) approved by the Food and Drug Administration (FDA) for the treatment of patients with relapsed follicular lymphoma. Fulvestrant is a selective ER degrader (SERD) and is FDA-approved to treat HR+ metastatic breast cancer.
 
The Phase 3 SOLAR-1 trial demonstrated the efficacy of the PI3K-α specific inhibitor alpelisib in combination with fulvestrant in the treatment of PIK3CA-mutated, hormone receptor HR+ advanced or metastatic breast cancer refractory to hormone regimen (1). Given the findings of the SOLAR-1 trial, we hypothesize that the clinical benefit of the PI3K pathway inhibitors and endocrine therapy combination can be extended to other HR+ solid cancers harboring alterations that activate the PI3K pathway. Estrogen and/or progesterone receptors are commonly expressed in the ovarian, endometrial, salivary

Proprietary Information of MD Anderson

Protocol 2020-1241

19 October 2022

[figure not shown]
	
gland, and other cancers (2). Furthermore, we and others found that PIK3CA mutations frequently co-occur in these HR-expressing cancers (3-8). Endocrine therapies, including fulvestrant, have been investigated for use in the treatment of gynecological malignancies and have demonstrated modest single-agent clinical activity (9-11). Similar to breast cancer, efficacy is limited by de novo and acquired endocrine resistance, and endocrine resistance can be overcome by PI3K pathway inhibition (12-14). In addition, our group and others have demonstrated that combinations of mammalian target of rapamycin (mTOR) inhibitors with hormone therapy can be effective in gynecological malignancies (14, 15).

Study Design:	We propose to conduct a multi-arm, open-label, phase 2 basket trial investigating the efficacy and safety of copanlisib in combination with fulvestrant in patients with selected HR+ advanced or metastatic solid cancers, harboring PI3K or PTEN alterations including ovarian cancer (cohort 1), endometrial cancer (cohort 2), and breast cancer (cohort 3). 
Study Population:	The study population will consist of subjects with selected HR+ (ER+ or/and PR+) advanced or metastatic solid tumors with PI3K (PIK3CA , PIK3R1) and/or PTEN alterations with ovarian, endometrial and breast cancer. Patients must have no available standard

Proprietary Information of MD Anderson

Protocol 2020-1241

19 October 2022

therapy known to prolong survival or are not candidates for such a therapy. The study

Key Inclusion Criteria	1. Histologically confirmed ER+ and/or PR+ advanced or metastatic solid cancer including ovarian cancer (cohort 1), endometrial cancer (cohort 2), or breast cancer (cohort 3) (Figure 1). ER and/or PR positivity is defined as >10% immunohistochemical staining of any intensity. Cohort 3 will be enriched to include at least 7 patients naïve to any PI3Ki in Stage 1 and also in Stage 2. 2. Presence of one or more PI3K and/or PTEN alterations in tumor tissue. Genetic alterations will include PIK3CA gain of function mutations, PIK3R1 loss of function mutations, PTEN loss of function mutations, and PTEN deletions. 3. Measurable disease per the RECIST 1.1. 4. The patient (or legally acceptable representative, if applicable) provides written informed consent for the study. 5. Female or male ≥ 18 years of age on the day of informed consent signing. 6. Patients have no available standard therapy known to prolong survival. For cohort 3 only, prior treatment with aPI3Ki or everolimus is not required and patients with or without prior PI3Ki or everolimus will be qualified for enrollment 7. Adequate archived tumor tissue for the analysis for PI3K and PTEN alterations if available. 8. Eastern Cooperative Oncology Group (ECOG) performance status of ≤ 2 . 9. Adequate organ and marrow function as defined below: a. Hemoglobin ≥ 9.0 g/dL b. Absolute neutrophil count $\geq 1.5 \times 10^9$ /L c. Platelet count $\geq 100 \times 10^9$ /L
------------------------	---

Proprietary Information of MD Anderson

Protocol 2020-1241

19 October 2022

	
d. Total bilirubin (TB) $\leq 1.5 \times$ institutional upper limit of normal (ULN); Patients with known Gilbert's disease who have TB $\leq 3 \times$ ULN may be enrolled)e. Aspartate transaminase (AST)/ alanine transaminase (ALT) $\leq 3 \times$ ULN. If patient has liver metastases, AST and ALT $\leq 5.0 \times$ ULN.f. Creatinine $\leq 1.5 \times$ ULNg. International normalized ratio ≤ 1.5. 
10. Fasting blood glucose ≤ 140 mg/dL and hemoglobin A1c $\leq 8.5\%$ (both criteria have to be met).
 
11. Cardiac ejection fraction $\geq 45\%$.
 
12. Women of childbearing potential must have a negative serum or urine pregnancy test (minimum sensitivity 25 IU/L or equivalent units of human chorionic gonadotropin [HCG]) within 14 days prior to the initiation of treatment and/or postmenopausal women must be amenorrheic for at least 12 months to be considered of non-childbearing potential. Women of childbearing potential (WOCBP) must agree and commit to the use of 2 highly effective methods of birth control throughout the duration of the study until at least 150 days following the last dose of study drug. Acceptable methods are defined as those that result, alone or in combination, in a low failure rate (i.e., less than 1% per year) when used consistently and correctly, such as surgical sterilization, an intrauterine device, or hormonal contraception in combination with a barrier method. Women using systemically acting hormonal contraceptives should add a barrier method. In certain countries (if permitted by law), WOCBP may agree to abide by heterosexual sexual abstinence during the time of participation in this study.
 
13. Male patients and their female partners of childbearing potential must agree and commit to use a barrier contraception (eg, condom with spermicidal foam/gel/film/cream/suppository) throughout the duration of the study until at least 90 days following the last dose of study drug, in addition to their female partners using either an intrauterine device or hormonal contraception and continuing until at least 90 days following the last dose of study drug. This criterion may be waived for male patients who have had a vasectomy > 6 months before signing the ICF.
 
14. Willing and able to comply with the protocol for the duration of the study including undergoing treatment and scheduled visits and examinations.

Key Exclusion Criteria	
1. The patient has central nervous system (CNS) involvement. If the patient fulfills the following 3 criteria, she/he is eligible for the study:
a. Completed prior therapy (including radiation and/or surgery) for CNS metastases, andb. CNS tumor is radiologically stable for ≥ 28 days prior to study start, andc. The patient is not receiving steroids and enzyme-inducing antiepileptic medications for brain metastases.2. Patients with HER2 positive breast cancer.

Proprietary Information of MD Anderson

Protocol 2020-1241

19 October 2022

	
3. Patients must be ≥ 4 weeks or at least 5 half-lives beyond treatment with any chemotherapy or other investigational therapy including hormonal, biological, or targeted agents at the time of treatment initiation.
- NOTE: If the patient received major surgery, she/he must have recovered adequately from the toxicity and/or complications from the intervention prior to starting the study treatment.4. Prior treatment with fulvestrant or any PI3Ki for cohorts 1 and 2.5. Known hypersensitivity to copanlisib or fulvestrant, or to any of the excipients of copanlisib or fulvestrant.6. Concomitant use of strong cytochrome P450 (CYP)3A4 inducers (e.g., rifampicin, phenytoin, carbamazepine, phenobarbital, St. John's wort) or inhibitors (e.g., ritonavir, saquinavir, nelfinavir, boceprevir, telaprevir, ketoconazole, omeprazole). Use of strong inhibitors and/or inducers of CYP3A4 is not permitted from Day -14 of Cycle 1 until the start of the study intervention.7. The patient is currently receiving warfarin or other coumarin derived anticoagulants for treatment, prophylaxis, or otherwise. Therapy with heparin, low molecular weight heparin, fondaparinux, or direct oral anticoagulants such as rivaroxaban or apixaban is allowed.8. Known additional malignancy that is progressing or requires active treatment.9. History or current evidence of any condition, therapy, or laboratory abnormality that might confound the results of the study, interfere with the patient's participation for the full duration of the study or is not in the best interest of the patient to participate, in the opinion of the treating investigator.10. Known psychiatric or substance abuse disorders that would interfere with cooperation with the requirements of the study.11. Known history of human immunodeficiency virus infection.12. History or current symptomatic pneumonitis.13. Has clinically significant, uncontrolled heart disease and/or recent cardiac events, including any of the following:
a. History of angina pectoris, symptomatic pericarditis, or myocardial infarction within 12 months prior to study entryb. History of documented congestive heart failure (New York Heart Association functional classification III-IV)c. Documented cardiomyopathyd. History of any cardiac arrhythmias, e.g., ventricular, supraventricular, nodal arrhythmias, or conduction abnormality in the previous 12 monthse. Uncontrolled hypertension defined by a systolic blood pressure (BP) ≥ 140 mmHg and/or diastolic BP ≥ 90 mmHg, with or without antihypertensive medication over the course of one clinic visit at intervals of ≥ 30 minutes. Initiation or adjustment of antihypertensive medication(s) is allowed prior to screening.14. Type 1 diabetes mellitus.15. Uncontrolled type 2 diabetes mellitus.
--	--

Proprietary Information of MD Anderson

Protocol 2020-1241

19 October 2022

	
16. Positive cytomegalovirus (CMV) polymerase chain reaction (PCR) test at baseline.
 
17. Active hepatitis B virus (HBV; chronic or acute; defined as having a known positive hepatitis B surface antigen [HbsAg] test at the time of screening) or hepatitis C infection requiring treatment.
 
• Participants with past HBV infection or resolved HBV infection (defined as the presence of hepatitis B core antibody [HbcAb] and absence of HbsAg) are eligible if HBV DNA is negative.• Participants with positive for hepatitis C virus (HCV) antibody are eligible only if PCR is negative for HCV RNA.
Study endpoints:	
Efficacy endpoints:
 
Radiographic tumor assessments (computed tomography [CT] scan or magnetic resonance imaging [MRI]) will be performed by RECIST 1.1. The endpoints of efficacy assessment include:
 
• ORR described as the proportion of patients who achieve CR or PR by the combination therapy.• PFS described as the time from study treatment initiation to the date of disease progression or death due to any cause. Patients without progression will be censored at the time of the last follow up.• OS described as the time from study treatment initiation to the date of death due to any cause. Patients without progression will be censored at the time of the last follow up. 
Safety endpoints:
 
• Incidence of AEs including but not limited to treatment-emergent AEs, serious AEs, deaths, and clinical laboratory abnormalities, as assessed by the National Cancer Institute (NCI) Common Terminology Criteria for Adverse Events (CTCAE) v5.0.• DLT is defined as any of the following adverse reaction observed during first cycle of treatment, and assessed as possibly, probably or definitely related to treatment with copanlisib in combination with fulvestrant. NCI CTCAE v. 5.0 will be used for grading of AEs.
○ Non-hematological AEs:

Proprietary Information of MD Anderson

Protocol 2020-1241

19 October 2022

	
▪ Grade ≥2 non-infectious pneumonitis▪ Laboratory abnormalities meeting Hy's law criteria (AST or ALT >3 × ULN with concomitant TB >2 × ULN). (FDA 2009)▪ Any ≥Grade 3 AE, except:
• Grade 3 fatigue lasting ≤5 days• Grade 3 nausea or vomiting that has resolved to grade ≤ 2 within 3 days after standard antiemetic therapies• Grade 3 diarrhea that has resolved to grade ≤2 within 3 days after standard antidiarrheal therapies• Isolated laboratory findings not associated with signs or symptoms and lasting less than 3 days, including but not limited to grade 3/4 alkaline phosphatase, uric acid, amylase, and lipase elevations, and grade 3 electrolyte laboratory abnormalities hypophosphatemia, hypokalemia, hypocalcemia, or hypomagnesemia responsive to supplementation and grade 3/4 lymphopenia.• Grade 3 hyperglycemia lasting ≤7 days○ Hematological AEs:
▪ Grade 4 neutropenia lasting ≥7 consecutive days▪ Grade 3 and grade 4 febrile neutropenia▪ Grade 4 anemia (in the absence of disease progression in bone marrow)▪ Grade 3 anemia requiring blood transfusion▪ Grade 4 thrombocytopenia of any duration▪ Grade 3 thrombocytopenia lasting ≥7 consecutive days or associated with bleeding○ The following event is classified as a DLT:
▪ If a full cycle of copanlisib (3 doses) will not be completed due to any study intervention-related AE, the AE is considered as a DLT▪ A delay of over 1 week in initiating Cycle 2 of copanlisib and/or fulvestrant treatment occurs secondary to any study drug related AE, the AE will be considered a DLT
--	--

Proprietary Information of MD Anderson

Protocol 2020-1241

19 October 2022

- Death not clearly attributed to underlying disease or alternative cause

Note: Allergic reactions leading to discontinuation of study interventions will not be considered as a DLT and participant will be replaced.

Exploratory endpoints:

Biomarker-based studies will be conducted using tumor tissue and liquid biopsies to assess clonal evolution, and mechanisms of innate and adaptive resistance.

Tumor biopsies, if medically feasible, will be obtained at screening (within 28 days of Cycle 1, Day 1), on-treatment after fulvestrant and copanlisib administration on Cycle 2 Day 1, and at End-of-treatment (EOT). Tumor biopsies will be optional but encouraged, especially in patients with a response or prolonged disease control (**Figure 2 and Appendix A: Schedule of Assessments**). Examples of studies include identification of genomic biomarkers of response and intrinsic or adaptive resistance by whole exome, targeted next-generation sequencing (NGS), Nanostring DSP, or other similar methods.

Mandatory blood samples to isolate plasma ctDNA will be collected at pre-treatment (Day -28 to Day 1 of Cycle 1), on-treatment (pre-dose -at the same time as the on treatment biopsy- on Cycle 2 Day 1 as well as at the first two restaging visits), and post-treatment at EoT. (**Figure 2 and Appendix A: Schedule of Assessments**).

Plasma ctDNA samples will be used to evaluate changes in ctDNA quantity and clonal evolution by selected molecular methods that may include targeted NGS, methylation sequencing, and droplet digital polymerase chain reaction..

Proprietary Information of MD Anderson

Protocol 2020-1241

19 October 2022

[figure not shown]
Duration of the study	Patients will receive the combination treatment until disease progression, unacceptable toxicity, death, withdrawal of consent, or discontinuation from the study treatment for any other reason.
------------------------------	---

Proprietary Information of MD Anderson

Protocol 2020-1241

19 October 2022

	Patients will be eligible to receive study treatment for as long as the investigator, the sponsor, and the supporting company agree that the patient is showing clinical benefit.
--	---

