5.4 Exclusion Criteria

Patients eligible for this study must not meet any of the following criteria:

Proprietary Information of MD Anderson

Protocol 2020-1241

19 October 2022

1. The patient has CNS involvement. If the patient fulfills the following 3 criteria, she/he is eligible for the study:
 - a. Completed prior therapy (including radiation and/or surgery) for CNS metastases, and
 - b. CNS tumor is radiologically stable for ≥ 28 days prior to study start, and
 - c. The patient is not receiving steroids and enzyme-inducing antiepileptic medications for brain metastases.
2. Patients with HER2 positive breast cancer.
3. Patients must be ≥ 4 weeks or at least 5 half-lives beyond treatment with any chemotherapy or other investigational therapy including hormonal, biological, or targeted agents at the time of treatment initiation.
 - NOTE: If the patient received major surgery, she/he must have recovered adequately from the toxicity and/or complications from the intervention prior to starting the study treatment.
4. For cohorts 1 and 2 prior treatment with fulvestrant or any PI3Ki.
5. Known hypersensitivity to copanlisib or fulvestrant, or any of the excipients of copanlisib or fulvestrant.
6. Concomitant use of strong CYP3A4 inducers (e.g., rifampicin, phenytoin, carbamazepine, phenobarbital, St. John's wort) or inhibitors (e.g., ritonavir, saquinavir, nelfinavir, boceprevir, telaprevir, ketoconazole, omeprazole). Use of strong inhibitors and/or inducers of CYP3A4 is not permitted from Day -14 of Cycle 1 until the end of the study treatment. (See **Appendix F: Strong Inhibitors or Strong Inducers of CYP3A4**)
7. The patient is currently receiving warfarin or other coumarin derived anticoagulants for treatment, prophylaxis, or otherwise. Therapy with heparin, low molecular weight heparin, fondaparinux, or direct oral anticoagulants such as rivaroxaban or apixaban is allowed.
8. Known additional malignancy that is progressing or requires active treatment.
9. History or current evidence of any condition, therapy, or laboratory abnormality that might confound the results of the study, interfere with the patient's participation for the full duration of the study or is not in the best interest of the patient to participate, in the opinion of the treating investigator.
10. Known psychiatric or substance abuse disorders that would interfere with cooperation with the requirements of the study.
11. Known history of human immunodeficiency virus infection.

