6.4.1 Prohibited Medications/Therapies

Use of the following concomitant medications/therapies is prohibited during the study:

- Any chemotherapy, radiation therapy, immunotherapy, hormone, or biologic therapy for cancer treatment other than that under investigation in this study.
Exceptions include the following:
 - Palliative radiotherapy is allowed during the study if the patient is otherwise benefitting from the study treatment in the opinion of the investigator. Study treatment should be discontinued for a minimum of 3 days before a patient undergoes palliative radiation treatment. Study treatment should be restarted within 28 days as long as any bone marrow toxicity has recovered.

Proprietary Information of MD Anderson

Protocol 2020-1241

19 October 2022

- Concomitant use of herbal preparations containing CYP3A4 inducers (e.g. St John's Wort) is not permitted during the study.
- Grapefruit and grapefruit juice (a CYP3A4 inhibitor) consumption is not permitted during the study.
- **The use of systemic corticosteroids or immunosuppressants after starting the study intervention should be avoided, except:**
 - (1) If a participant is on chronic corticosteroid therapy, e.g. replacement therapy such as physiologic corticosteroid replacement therapy for adrenal or pituitary insufficiency (in dosing not exceeding 10 mg daily of prednisone equivalent) is not considered a form of systemic treatment.
 - (2) Systemic corticosteroids above 10 mg prednisolone or equivalent or other immunosuppressants may be allowed after starting the study intervention for the management of acute conditions (e.g. treatment of non-infectious pneumonitis) or as premedication for radiological contrast infusion as clinically indicated.

Participants may be using inhaled or topical steroids. For more information about steroid use in management of skin toxicities, please refer to **6.3.1.4**.

If treatment with a prohibited medication/therapy is necessary, the patient will be withdrawn from the study after discussion with the sponsor.

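### Exclusion Criterion 6 ends the restriction on strong CYP3A4 inhibitors and inducers at treatment start in the synopsis but at treatment end in Section 5.4

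*Combined protocol and SAP*

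**What the plan says.** Key Exclusion Criterion 6 in the Clinical Study Synopsis excludes patients on strong CYP3A4 inducers or inhibitors, gives examples of each, and closes with a dated sentence, under which use of these agents "is not permitted from Day -14 of Cycle 1 until the start of the study intervention".

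Item 6 of Section 5.4 (Exclusion Criteria) repeats the criterion with the same classes and examples, but its dated sentence reads: "Use of strong inhibitors and/or inducers of CYP3A4 is not permitted from Day -14 of Cycle 1 until the end of the study treatment". It then refers the reader to Appendix F for the agents.

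The on-study list in Section 6.4.1 (Prohibited Medications/Therapies) touches CYP3A4 in two places. "Concomitant use of herbal preparations containing CYP3A4 inducers" is barred during the study, with St John's wort as the example. The other item is: "Grapefruit and grapefruit juice (a CYP3A4 inhibitor) consumption is not permitted during the study". The section ends with a rule that a patient who needs a prohibited medication or therapy is withdrawn from the study after discussion with the sponsor.

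**The concern.** A site has to know whether a strong CYP3A4 modulator may be started once a patient is on treatment. Section 5.4 answers this directly. The synopsis gives a restriction that has already lapsed by then. If the drug counts as prohibited, the withdrawal rule in Section 6.4.1 applies; if it does not, the patient may stay on study. Two patients in the same situation could therefore be handled differently.

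Part 1 is where this could matter most. The study advances to Part 2 only if no more than 1 DLT is seen (Section 5), and Part 1 patients are carried into the primary analysis of objective response (Section 2.2). A single DLT in a patient taking a strong modulator could bear on that decision. Such patients would also be hard to find afterwards: Section 6.4 puts concomitant medication in the electronic medical record and not in the electronic case report forms.

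**Working it through.** No sample size, power or error rate is involved, so the check is a comparison of the passages and of the length of each window.

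1. **Is it the same criterion?** Yes. Both are item 6 of the exclusion criteria, both name strong inducers and strong inhibitors with the same examples, and both start the dated restriction at Day -14 of Cycle 1. Section 5.4 adds the pointer to Appendix F.

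2. **Where do they differ?** Only in the end point: the start of the intervention in the synopsis, the end of treatment in Section 5.4. Both sentences are complete and current, and neither is cut by a redaction.

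3. **How far apart are the windows?** The synopsis window runs from Day -14 to the first dose, about 14 days. The Section 5.4 window is about 14 + 28k days for a patient treated for k whole 28-day cycles:
   - k = 1 (the Part 1 DLT period): 14 + 28 = 42 days, against 14.
   - k = 2 (the minimum to be evaluable in Part 2): 14 + 56 = 70 days, against 14.
   - There is no upper limit, because Section 6.10 sets no maximum number of cycles.

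4. **Does other visible text settle the end point?**
   - Section 6.4.1 covers herbal inducers and grapefruit. It does not list strong inhibitors or inducers as drug classes, so examples in the criterion such as ritonavir, ketoconazole, rifampicin, phenytoin and carbamazepine are not named there. St John's wort is an example in the criterion and is barred throughout the study by Section 6.4.1, so for that agent the synopsis window is also shorter than the on-study rule.
   - Section 6.3.1.3 asks for caution with verapamil and diltiazem, which it calls moderate CYP3A4 inhibitors, because of a possible interaction. It does not address strong agents.
   - The visible sentence of Section 6.4.2 deals only with copanlisib and fulvestrant acting on each other.
   - No visible clause says whether the synopsis or the body of the protocol prevails.
   - The content of Appendix F is not shown.

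5. **Can the effect be sized?** Not from the visible text, which speaks only of a potential interaction and gives no figure for the change in copanlisib exposure.

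**The case against.** The strongest reply is that the two versions do not conflict in substance. A reader might infer that the synopsis allows a strong modulator throughout treatment, and so states the opposite rule. The documents do not support that. The synopsis sentence stops at treatment start and is silent afterwards; it grants no permission. In both versions the criterion opens by excluding concomitant use, which can be read as reaching into treatment. Sections 6.4.1 and 6.3.1.3 show that some CYP3A4 agents are restricted or cautioned against on treatment. This stands: the synopsis gives a shorter window, not a contrary permission. It does not remove the mismatch, because the synopsis states an explicit end point that differs from the one in Section 5.4.

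A second reply is that the public copy is incomplete. Appendix F is not visible, and the abbreviation list defines transporter and pharmacokinetic terms that do not appear in the visible body, so interaction text may have been removed. A fuller on-study rule may exist in the complete protocol. This also stands, and it limits what can be said about Section 6.4.1. It would not make the two criteria agree.

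A third reply concerns consequences. A reader might infer that copanlisib exposure, DLTs and response would in fact be altered, or that two different lists of protocol deviations would result. The visible text gives no interaction size and no definition of a protocol deviation, so these remain possibilities only.

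**Conclusion.** The point holds as an internal inconsistency: one exclusion criterion has two end points, and nothing visible says which governs. The gap is about 14 days of restriction against about 14 days plus all of treatment. The consequence is that the status of a strong CYP3A4 modulator started during treatment, and with it the withdrawal rule, depends on the page read. An effect on copanlisib exposure and on Part 1 DLT assessment is possible but is not quantified in the visible documents.

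The mismatch itself rests on no assumption beyond the two sentences as printed. The statement that Section 6.4.1 does not settle it rests on the visible text alone. The point should be corrected, but it does not touch the sample size or the planned analyses.

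**What to change.** Reconcile the end point of the restriction between synopsis Key Exclusion Criterion 6 and Section 5.4 item 6, so that both state the same period. Then check that Section 6.4.1 and Appendix F are consistent with it, so that it is clear whether the withdrawal rule applies to a strong modulator started during treatment.

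The lists of agents need not be identical. An on-study list may properly include items, such as grapefruit and herbal inducers, that an eligibility criterion does not. Which window is right is a clinical decision for the sponsor and is left open here.

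The cost is a wording change in an amendment, with no change to the design or the analysis.
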